3.2.1.3. Dose-Limiting Toxicities (DLT)

A DLT is defined as any TEAE not attributable to disease or disease-related processes or to concomitant medications or procedures that occurs during the DLT-evaluation period (Cycle 0, Day 1 to Cycle 1, Day 21 of Dose Escalation) and is Grade 3 or above, according to NCI-CTCAE version 5.0, with the exceptions as defined below.

For hematological toxicities, a DLT is defined as follows:

Hematologic Dose-Limiting Toxicities (DLT) NCI-CTCAE version 5.0		
Hematological toxicity	NCI-CTCAE Grade	CTCAE version 5.0 Definition
Neutrophil count decreased	4 (Lasting > 7 days or neutrophil count decreased that requires supportive therapy with myeloid growth factors)	< 500/mm ³ ; < 0.5 × 10 ⁹ /L
Febrile neutropenia	≥ 3	Grade 3: ANC < 1000/mm ³ with a single temperature of > 38.3°C or a sustained temperature of ≥ 38°C for more than one hour Grade 4: Life-threatening consequences; urgent intervention indicated
Anemia	4	Life-threatening consequences; urgent intervention indicated
Platelet count decreased	≥ 3 Lasting > 7 days or with clinically significant hemorrhage	Grade 3: < 50,000 – 25,000/mm ³ ; < 50.0 – 25.0 × 10 ⁹ /L Grade 4: < 25,000/mm ³ ; < 25.0 × 10 ⁹ /L
Lymphocyte count decreased	4 Lasting ≥ 14 days	< 200/mm ³ ; < 0.2 × 10 ⁹ /L
Any	5	Death

For hepatic organ toxicities, a DLT is defined as follows:

Hepatic Dose-Limiting Toxicities (DLT) NCI-CTCAE version 5.0		
Hepatic Organ Toxicity	NCI-CTCAE Grade	CTCAE version 5.0 Definition
Serum aspartate aminotransferase (AST) increase	4	> 20.0 × the upper limit normal (ULN) if baseline was normal; > 20.0 × baseline if baseline was abnormal
Serum alanine aminotransferase (ALT) increase	4	> 20.0 × ULN if baseline was normal; > 20.0 × baseline if baseline was abnormal
AST or ALT increased	3 Lasting >5 days	> 5.0 – 20.0 × ULN if baseline was normal; > 5.0 – 20.0 × baseline if baseline was abnormal
ALT or AST increased $\geq 3.0 \times$ ULN with simultaneous TBL increased $\geq 2.0 \times$ ULN	Not applicable	Not applicable
Any	5	Death

For pulmonary toxicities, a DLT is defined as any of the following:

Pulmonary Dose-Limiting Toxicities (DLT) NCI-CTCAE version 5.0		
Pulmonary Toxicity	NCI-CTCAE Grade	CTCAE version 5.0 Definition
Confirmed interstitial lung disease (ILD)	1	Asymptomatic; clinical or diagnostic observations only; intervention not indicated
	2	Symptomatic; medical intervention indicated; limiting instrumental activities of daily living (ADL)

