	3	Severe symptoms; limiting self care ADL; oxygen indicated
	4	Life-threatening respiratory compromise; urgent intervention indicated (eg., tracheotomy or intubation)
	5	Death
Any other pulmonary toxicity	≥ 3	Grade 3: Severe or medically significant but not immediately life-threatening; hospitalization or prolongation of

		existing hospitalization indicated; limiting self care ADL Grade 4: Life-threatening consequences; urgent intervention indicated Grade 5: Death
--	--	---

For non-hematological, non-hepatic, or non-pulmonary organ toxicities (ie, any other Grade ≥ 3 non-hematologic, non-hepatic, non-pulmonary toxicities including Grade 5 events), a DLT is defined as any of the following:

Dose-Limiting Toxicities (Non-Hematologic, Non-Hepatic, Non-Pulmonary Toxicities)		
DLT	NCI-CTCAE Grade	CTCAE version 5.0 Definition
Symptomatic heart failure	2	Symptoms with moderate activity or exertion
	3	Symptoms at rest or with minimal activity or exertion; hospitalization; new onset of symptoms
Left ventricular ejection fraction (LVEF)	3	Resting ejection fraction (EF) 39 – 20%; $\geq 20\%$ drop from baseline
Endocrine toxicities	≥ 3 Which do not resolve in ≤ 14 days	Grade 3: Severe or medically significant but not immediately life-threatening; hospitalization or prolongation of existing hospitalization indicated; limiting self care ADL Grade 4: Life-threatening consequences; urgent intervention indicated

The following TEAEs are considered DLTs
Thrombocytopenia requiring transfusion. Anemia requiring transfusion Inability to complete at least 75% of the prescribed doses (ie, at least 42 doses of DS-1205c and 16 doses of gefitinib) in the 7 days of Cycle 0 and the 21 days of Cycle 1 as a result of Grade ≥ 2 AE not attributed to disease.

The following TEAEs are NOT considered DLTs:

The following TEAEs are NOT considered Dose Limiting Toxicities		
TEAE	NCI-CTCAE Grade	CTCAE version 5.0 Definition
Fatigue	3 Lasting \leq 7 days	Fatigue not relieved by rest, limiting self care ADL
Nausea	3 That resolves to \leq grade 2 in 48 hours	Inadequate oral caloric or fluid intake; tube feeding, TPN, or hospitalization indicated
Vomiting	3 That resolves to \leq grade 2 in 48 hours	Tube feeding, TPN, or hospitalization indicated
Diarrhea	3 That resolves to \leq grade 2 in 48 hours	Increase of \geq 7 stools per day over baseline; hospitalization indicated; severe increase in ostomy output compared to baseline; limiting self care ADL

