5.4. Dose Interruptions and Reductions

Following the DLT evaluation period (Section 3.2.1.3), the Investigator will evaluate which toxicities are attributed to the study drug and adjust the administration schedule of the drug. [Table 5.1](#) outlines schedule modifications for specific toxicities. Doses may also be interrupted for other toxicities per Investigator discretion, and supportive medication may be administered in accordance with local practice guidelines. All interruptions must be recorded on the drug administration electronic Case Report Form (eCRF).

In the event of a dose delay occurring prior to completion of a PK blood sampling in the study, Investigators should contact Sponsor medical monitor or designee for guidance regarding scheduling of these procedures.

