5.4.1. Dose Interruptions

During the DLT evaluation period, the administration of study drugs may be interrupted due to DLTs for up to 21 days according to the rules listed in [Table 5.1](#) below. When a DLT triggered interruption is required, both DS-1205c and gefitinib should be held. If a subject requires a dosing delay longer than 21 days, the subject will be withdrawn from the study.

For non-DLT TEAEs Grade 3 and above, study medications will be withheld for up to 3 weeks until improvement of the TEAE to Grade 2 or below. Study medications may be resumed after discussion and agreement between the Investigator and Sponsor. If the dosing interruption exceeds 21 days, the subject will be withdrawn from the study.

Table 5.1: Dose Interruption and Dose Resumption Criteria

	Worst toxicity NCI-CTCAE v5.0 Grade (unless otherwise specified) by Definition	Schedule modification for DS-1205c and gefitinib
General disorders and administration site conditions		
Fatigue/ Generalized muscle weakness	Grade 3 (Fatigue not relieved by rest, limiting self care ADL)	Delay study medications until resolved to \leq Grade 2, then: 
 • If resolved in \leq 7 days, resume study medications. • If resolved in $>$ 7 days and \leq 21 days, study medications may be resumed after discussion and agreement between the Investigator and Sponsor. • If not resolved in $>$ 21 days, discontinue subject from treatment.
Blood and lymphatic system disorders		
Neutrophil count decreased	Grade 3 ($< 1000-500/\text{mm}^3$; $< 1.0 - 0.5 \times 10^9/\text{L}$) Grade 4 ($< 500/\text{mm}^3$; $< 0.5 \times 10^9/\text{L}$)	Delay study medications until resolved to \leq Grade 2, then: 
 • If resolved in \leq 7 days, resume study medications. • If resolved in $>$ 7 days and \leq 21 days, study medications may be resumed after discussion and agreement between the Investigator and Sponsor. • If not resolved in $>$ 21 days, discontinue subject from treatment.
Febrile neutropenia	Grade 3 ($\text{ANC} < 1000/\text{mm}^3$, with a single temperature $> 38.3^\circ\text{C}$ or a sustained temperature of $\geq 38^\circ\text{C}$ for more than one hour) Grade 4 (Life-threatening consequences; urgent intervention indicated)	Delay study medications until neutrophil count decreased resolved to \leq Grade 2. Study medications may be resumed after discussion and agreement between the Investigator and Sponsor.

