Table 5.1: Dose Interruption and Dose Resumption Criteria (Continued)

	Worst toxicity NCI-CTCAE v5.0 Grade (unless otherwise specified) by Definition	Schedule modification for DS-1205c and gefitinib
Lymphocyte count decreased	Grade 3 (<500 - $200/\text{mm}^3$; <0.5 - $0.2 \times 10^9/\text{L}$): Grade 4 ($<200/\text{mm}^3$; $<0.2 \times 10^9/\text{L}$)	Delay study medications until resolved to \leq Grade 2, then: 
 • If resolved in \leq 7 days, resume study medications. • If resolved in $>$ 7 days and \leq 21 days, study medications may be resumed after discussion and agreement between the Investigator and Sponsor. • If not resolved in $>$ 21 days, discontinue subject from treatment.
Anemia	Grade 3 ($\text{Hb} < 8.0 \text{ g/dL}$; $< 4.9 \text{ mmol/L}$; $< 80 \text{ g/L}$; transfusion indicated) Grade 4 (Life-threatening consequences; urgent intervention indicated)	Delay study medications until resolved to \leq Grade 2, then 
 • If resolved in \leq 7 days, resume study medications. • If resolved in $>$ 7 days and \leq 21 days, study medications may be resumed after discussion and agreement between the Investigator and Sponsor. • If not resolved in $>$ 21 days, discontinue subject from treatment.
Platelet count decreased	Grade 3 ($< 50,000$ - $25,000/\text{mm}^3$; < 50 - $25 \times 10^9/\text{L}$) Grade 4 ($< 25,000/\text{mm}^3$; $< 25.0 \times 10^9/\text{L}$)	Delay study medications until resolved to \leq Grade 2, then: 
 • If resolved in \leq 7 days, resume study medications. • If resolved in $>$ 7 days and \leq 21 days, study medications may be resumed after discussion and agreement between the Investigator and Sponsor. • If not resolved in $>$ 21 days, discontinue subject from treatment. Consider transfusion per institutional guidelines.

Table 5.1: Dose Interruption and Dose Resumption Criteria (Continued)

	Worst toxicity NCI-CTCAE v5.0 Grade (unless otherwise specified) by Definition	Schedule modification for DS-1205c and gefitinib
Cardiac Disorders		

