Diarrhea/Colitis	Grade 3 (Increase of \geq 7 stools per day over baseline; hospitalization indicated; severe increase in ostomy output compared to baseline; limiting self care ADL)	Delay study medications until resolved \leq Grade 2, and consider anti-diarrheal treatment per local practice/guidelines, then: 
 • If resolved in \leq 7 days, resume study medications. • If resolved in $>$ 7 days and \leq 21 days, study medications may be resumed after discussion and agreement between the Investigator and Sponsor. • If not resolved in $>$ 21 days, discontinue subject from treatment.
	Grade 4 (Life-threatening consequences; urgent intervention indicated)	Discontinue subject from study treatment.

Table 5.1: Dose Interruption and Dose Resumption Criteria (Continued)

	Worst toxicity NCI-CTCAE v5.0 Grade (unless otherwise specified) by Definition	Schedule modification for DS-1205c and gefitinib
Other laboratory AEs	Grade 3	
Delay study medications until resolved to \leq Grade 2, then:
 
 • If resolved in \leq 7 days, resume study medications • If resolved in $>$ 7 days and \leq 21 days, study medications may be resumed after discussion and agreement between the Investigator and Sponsor. • If not resolved in $>$ 21 days, discontinue subject from treatment.
	Grade 4	Discontinue subject from study treatment

ABG = arterial blood gas; ANC = absolute neutrophil count; ALT = alanine aminotransferase; AST = aspartate aminotransferase; CTCAE: Common Toxicity Criteria for Adverse Events; DLCO = diffusing capacity of the lungs for carbon monoxide; ECHO = echocardiogram; eCRF = electronic Case Report Form; g/dL = grams per deciliter; Hb = hemoglobin; HRCT = high-resolution computed tomography; ILD = interstitial lung disease; L = liter; LVEF = left ventricular ejection fraction; ms = milliseconds; NCI = National Cancer Institute; QTcF = corrected QT using Fridericia's formula; TBL = total bilirubin; ULN = upper limit of normal.

A There will be no dose interruptions for Grade 1 to Grade 3 lymphopenia.

Possible exceptions to the above may be allowed on a case-by-case basis after discussion and agreement between Investigator and Sponsor. The agreement must be documented.

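### Table 5.1 tells sites both to hold and not to hold study drugs for Grade 3 lymphopenia, and nothing says which instruction governs

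*Combined protocol and SAP*

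**What the plan says.** Three places in Section 5.4.1 instruct sites on Grade 3 lymphopenia.

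- The general text: "For non-DLT TEAEs Grade 3 and above, study medications will be withheld for up to 3 weeks until improvement of the TEAE". The stated target for improvement is a grade no higher than 2.
- Table 5.1, row "Lymphocyte count decreased": Grades 3 and 4 are both listed, and both drugs are delayed until the count recovers to Grade 2 or lower.
- Footnote A under Table 5.1: "There will be no dose interruptions for Grade 1 to Grade 3 lymphopenia".

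The line after the footnote allows documented case-by-case exceptions agreed between Investigator and Sponsor.

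Two sentences bear on when the table applies. Section 5.4 introduces it for use after the DLT-evaluation period, when "the Investigator will evaluate which toxicities are attributed to the study drug and adjust the administration schedule of the drug". Section 5.4.1 brings it into that period for holds caused by DLTs: "During the DLT evaluation period, the administration of study drugs may be interrupted due to DLTs for up to 21 days".

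Section 3.2.1.3 defines a DLT as "any TEAE not attributable to disease or disease-related processes or to concomitant medications or procedures that occurs during the DLT-evaluation period" and is Grade 3 or above, subject to listed exceptions. It lists Grade 3 lymphocyte count among events that are not DLTs. It also counts as a DLT "Inability to complete at least 75% of the prescribed doses (ie, at least 42 doses of DS-1205c and 16 doses of gefitinib") over Cycles 0 and 1, when the cause is an AE of Grade 2 or higher not attributed to disease. Section 11.2 requires a subject without a DLT to have received at least 75% of the Cycle 1 doses to enter the DLT-Evaluable Set.

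**The concern.** A site that reads the row, or the general sentence, stops both drugs. A site that reads the footnote continues them. With about 20 sites planned, the same laboratory finding could be managed in opposite ways.

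During the first 28 days the choice may also matter for the primary endpoint. Missed doses feed the 75% completion rule in Section 3.2.1.3 and the 75% evaluability rule in Section 11.2. A long enough hold could therefore change how a subject is classified for an event that the protocol says is not itself dose-limiting. The 75% rule is not in question; the difficulty is that the missed doses would come from a hold that footnote A forbids.

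**Working it through.** **1. Reproduce the plan's thresholds.** DS-1205c is given twice daily for 7 + 21 = 28 days, so 56 doses; 0.75 × 56 = 42. Gefitinib is given once daily for the 21 days of Cycle 1, so 21 doses; 0.75 × 21 = 15.75, rounded up to 16. Both match Section 3.2.1.3.

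**2. Dose counts after a hold.** For a hold of h full days of both drugs inside Cycle 1, with no other missed doses, gefitinib is 21 − h, DS-1205c over 28 days is 56 − 2h, and DS-1205c in Cycle 1 is 42 − 2h.

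| Hold (days) | Gefitinib (need 16) | DS-1205c, 28 days (need 42) | DS-1205c, Cycle 1 | Share of Cycle 1 doses, either drug |
|---|---|---|---|---|
| 0 | 21 | 56 | 42/42 | 100% |
| 5 | 16 | 46 | 32/42 | 76.2% |
| 6 | 15 | 44 | 30/42 | 71.4% |
| 7 | 14 | 42 | 28/42 | 66.7% |

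Gefitinib is the binding limit. The 16-dose requirement and the Section 11.2 rule both fail at 6 days.

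**3. When a hold can cost 6 doses.** Six days must fit inside Cycle 1, so the latest start is Day 21 − 6 + 1 = Day 16. A hold starting on Day 17 loses at most 5.

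**4. How long a hold might last.** Scheduled Cycle 1 hematology after Day 1 is on Days 4, 8 and 15, then Cycle 2 Day 1, each ±1 day (Sections 6.1.3.2 and 6.1.3.3). Assume a hold starts on one draw day and dosing resumes on the next. The days lost within Cycle 1 are then:

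- Day 4 to Day 8: 4 (2 to 6 with windows)
- Day 8 to Day 15: 7 (5 to 9)
- Day 15 to Cycle 2 Day 1: 7 (5 to 8)

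Section 6.1 keeps subjects in hospital from Cycle 0 Day 2 to Cycle 2 Day 2, with discretionary leave after Cycle 1 Day 8, so unscheduled testing could shorten these.

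**5. What happens below 75%.**

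- If the event is recorded as an AE not attributed to disease, the completion rule points to a DLT and the list of exclusions points away from one. Section 3.2.1.3 gives no order between them.
- If no DLT is assigned, whether through disease attribution or because the exclusion prevails, Section 11.2 leaves the subject out of the DLT-Evaluable Set.
- Section 3.2.1.2 defines evaluability by minimum safety evaluation or a DLT. Section 3.2.1.3 removes subjects for missed doses only when the reason is unrelated to AEs. Under those two texts exclusion is not automatic.

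**6. Illustration of one reclassified subject.** This uses grid integration of the Section 11.11 model with its stated prior. It gives prior medians of 8.0% at 200 mg and 24.1% at 800 mg, against the stated approximate 8% and 24.5%. The cohorts are hypothetical. After 0/3 DLTs at 200 mg and 0/3 at 400 mg, the probability that the DLT rate at 600 mg exceeds 0.33 is 0.049. With 1/3 at 400 mg it is 0.292, above the 0.25 limit, so 600 mg would be barred.

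**The case against.** The best defence is that a specific footnote overrides a general sentence, so footnote A is simply the exception to Section 5.4.1. Against the general sentence alone that is a fair reading. It does not dispose of the lymphocyte row, which names the same toxicity and grade and orders the opposite. The footnote marker is not visible on any row in the text available, possibly because of PDF extraction. If it sits on the lymphocyte row, the footnote reads more naturally as a qualifier, but the Grade 3 entry in that row then has no function.

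A second objection concerns the DLT-evaluation period and largely stands. Table 5.1 is introduced for later use and enters that period only for DLT-triggered holds. If that scope excludes the row for a non-DLT event, it arguably excludes the footnote too, and Section 5.4.1 alone requires the hold. If the footnote does reach into the period, it is a specific exception. The row cannot be ruled out of the period and then used there to rebut the footnote. The direct conflict is between row and footnote; which of them applies to a non-DLT event inside the period is unclear.

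Third, a reader might infer that any hold of 6 days makes the subject a DLT. The documents do not support that. Section 9.1 lists when an isolated laboratory abnormality should be reported as an AE, and a dose interruption is not among the triggers. An asymptomatic low count that the Investigator does not judge to be an AE meets neither the Section 5.4.1 sentence nor the completion rule. Attribution to disease also takes the event outside the DLT definition, and the exclusion for Grade 3 lymphocyte count may prevail.

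Finally, the exception clause can settle individual subjects. It does not set the default that sites need.

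**Conclusion.** The inconsistency is real and the table is wrong as written: at Grade 3 the lymphocyte row and footnote A cannot both be followed, and nothing ranks them. After the DLT-evaluation period it affects treatment only. Within that period Section 5.4.1 alone may require the hold, and an effect on classification is conditional. It needs a hold that is actually followed, starts by Cycle 1 Day 16 and costs at least 6 days, leaving at most 15/21 gefitinib and 30/42 DS-1205c doses in Cycle 1 (71.4%). A DLT further needs AE recording, attribution other than to disease, and the completion rule prevailing over the exclusion. Otherwise the consequence is loss from the Section 11.2 set, which the definitions in Sections 3.2.1.2 and 3.2.1.3 do not clearly share.

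The stronger inference, that this flaw distorts dose escalation, is not supported: the documents give no frequency for Grade 3 lymphopenia, and in-hospital testing may keep holds short. This is a wording error worth correcting, with a possible but unquantified reach into the primary endpoint.

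**What to change.** Make footnote A the rule, since it agrees with the exclusion of Grade 3 lymphocyte count from the DLT definition.

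1. Delete Grade 3 from the "Lymphocyte count decreased" row of Table 5.1 and keep Grade 4.
2. Add an exception for Grade 3 lymphopenia to the Section 5.4.1 sentence on non-DLT events.
3. As an optional safeguard, exclude lymphocyte count from the Grade 3 entry of the "Other laboratory AEs" row, so that no one reads the hold back in through that row.

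These edits do not settle the order between the completion rule and the exclusion list, but they remove this route to the question.

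The cost is wording only. Data collection, the DLT definition and Section 11.2 are unchanged, and Grade 4 lymphopenia is still held. The downside is that subjects stay on drug during Grade 3 lymphopenia, as footnote A already intends.

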5.4.2. Dose Reductions

Dose reductions of DS-1205c and gefitinib may be permitted following a discussion between the Investigator and the Sponsor. The final decision should be documented and filed at the site.

No dose reductions of gefitinib will be allowed for DLT evaluation period of dose escalation part.

5.5. Prior and Concomitant Medications, Treatments, and Procedures

5.5.1. Prior Medication(s), Treatment(s), and Procedure(s)

All prior anticancer treatments or procedures (eg, surgery, radiation therapy, TKI therapy, chemotherapy, immune checkpoint inhibitor therapy) will be recorded. All medications taken by subjects within 22 days prior to the first dose of DS-1205c will be recorded as prior medications.

5.5.2. Concomitant Medication(s)

Concomitant medications, ie, medications used from the first dose of DS-1205c until 30 days after the last dose of study drug or the start of any new anticancer treatment, whichever comes first, will be recorded. All concomitant medications will be recorded on the eCRF.

Management of study drug-related AEs will be as per treating physician discretion and institutional guidelines.

Hematopoietic growth factors (HGFs) may be used for treatment based on the clinical judgment of the Investigator. HGFs (e.g. G-CSF.) should not be used prophylactically during the DLT evaluation period. Use of prophylactic HGFs may be considered after Cycle 1 following discussion with the Sponsor. (Treatment with HGFs for anemia associated with chemotherapy is not approved in Japan)

Bisphosphonates (eg, pamidronate or zolendronate) or denosumab for control of bone pain, treatment of bony metastases, or treatment of osteoporosis, may be used per clinical judgment of the Investigator and according to prescribing information and institutional guidelines.

5.5.3. Prohibited Medications

The following medications, treatments and procedures will be prohibited (with noted exceptions below) from enrollment until the End-of-Treatment (EOT) visit, in both Dose Escalation and Dose Expansion:

- Other anticancer therapy, including cytotoxic chemotherapy, targeted agents, immunotherapy, endocrine therapy, or TKIs (other than gefitinib)
- Other investigational therapeutic agents
- Radiotherapy (except for palliative radiation)
- Radiotherapy to the thorax
- Concomitant use of chronic systemic corticosteroids or other immunosuppressive medications (inhaled corticosteroids or intra-articular steroid injections are permitted in this study)
- The use of concomitant medications that prolong the QTc (See Section [17.6](#))
- Foods containing *Hypericum perforatum* (St. John's Wort)
- Foods or beverages containing grapefruit
- Use of gastric acid-reducing agents (eg, proton pump inhibitors or histamine 2 receptor antagonists)

Use of antacids is allowed. Any antacid should be used \geq 2 hours before or after DS-1205c dosing, and should be used \geq 6 hours before or after gefitinib dosing

- Strong CYP3A4 inducers (eg, phenytoin, carbamazepine, rifampin). (See Section 17.6)
- Avoid strong CYP3A4 inhibitors (eg, clarithromycin, itraconazole, ketoconazole, ritonavir, nefazodone, voriconazole) if possible. Medical judgment should be used when administering concomitant strong CYP3A4 inhibitors. (See Section 17.6)
- Avoid co-administration of UGT1A1 and UGT1A4 inhibitors (eg, valproic acid, probenecid) and inducers (eg, dexamethasone, phenobarbital, rifampicin) if possible. Medical judgment should be used when administering concomitant inhibitors or inducers of UGT1A1 and UGT1A4
- Avoid co-administration of BCRP substrates (eg, rosuvastatin) if possible. Medical judgment should be used when administering concomitant substrates of BCRP
- It is recommended that the starting and maintenance dose of statins should be as low as possible and should be guided by the statin label. Monitoring of low-density lipoprotein (LDL) cholesterol levels is advised. If the subject experiences any potentially relevant AEs suggestive of muscle toxicity including unexplained muscle pain, tenderness, or weakness, particularly if accompanied by malaise or fever, the statin should be stopped, CK level should be checked, and any appropriate further management should be taken
- Avoid co-administration of P-gp substrates (eg, digoxin) if possible. Medical judgment should be used when administering concomitant substrates of P-gp

Subjects who wear contact lenses must discontinue wearing their lenses if they have any mild to moderate eye symptoms (CTCAE Grade ≤ 2) while receiving treatment until at least one week after symptoms have resolved. If a subject has a recurrence of eye symptoms or experiences any severe (CTCAE Grade ≥ 3) ocular events they must discontinue wearing their contact lenses until at least one week after treatment is permanently discontinued. Subjects must not use any eye drops or ointment for treatment of eye symptoms, unless agreed by a study doctor, at any time during the study ≥ 1 week after permanent discontinuation of study treatment. Subject should consult the clinic promptly if they have any concerns.

Subjects taking warfarin should be monitored regularly for changes in prothrombin time or PT-INR.

